## 2. Study objectives

### a. Primary objective

The aim of our study is to determine the safety and efficacy of an early goal-directed preload and afterload decrement with a target systolic blood pressure of 90 mmHg to 110 mmHg by aggressive vasodilatation versus standard medical care in a non-ICU setting in patients with acute HF. The primary endpoint is **death or heart failure re-hospitalization** up-to 180 days of follow-up.

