## h. Study assessments

The following study assessments are planned:

Study assessment schedule	Screening	D1	D2	D3	D4	D5	D6	Discharge	FU	D90	D180	D360
Screening of Patient in Emergency Department	S/I											
Check Inclusion/ Exclusion Criteria	S/I											
Inclusion: Patient signed the Informed Consent	S/I											
Inclusion: Randomize Patient in Secu Trial	S/I											
No inclusion: Enter Patient in " Screening Enrolment Log"	S/I											
HF assessment	S/I											
Measure vital signs 0h/ 30min/ 1h/2h/3h/4h/6h	S/I											
Give oral Capsule of Nitroglycerine (1)		I										
Apply the nitro patches according to the blood pressure		I										
Increasing nitro patches according to BP, stick for 24hrs (2)			I									
Reduction of nitro patches according to BP (2)			I	I	I	I						
Give one oral Hydralazine Tbl à 25mg every 6hours		I										
Collect Urine and Blood Samples		S/I	S/I	S/I			S/I					
Dyspnea Assessment		S/I	S/I				S/I	S/I				
Edema measurement		S/I					S/I					
Hand out the QOL and KCCQ Questionnaire				S/I						S/I	S/I	S/I
Collected the QOL and KCCQ Questionnaire					S/I					S/I	S/I	S/I
Actively search for AE's/ SAE's			S/I	S/I			S/I			S/I	S/I	S/I
Ask about Patient's Health status										S/I	S/I	S/I
Ask for medication										S/I	S/I	S/I
Ask about Dyspnea										S/I	S/I	S/I
Rehospitalization (3)										S/I	S/I	S/I

S= Standard group/ I= Interventions group

(1) every 10min x 3times

(2) target systolic BP  $\leq$ 110mmHg

(3) SAE, yes/no?

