### **n. Per-protocol (PP)**

The per-protocol population PP consists of all patients randomized, who received at least one dose of the study drug (Hydralazine and/or nitrates in the form of capsules, spray and/or transdermal application) and had a baseline plus follow-up assessment (180 days) of the primary endpoint completing the study without major protocol deviations. PP analyses are planned as part of sensitivity analyses.

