### **p. Safety population**

For the analysis of safety, including protocol pre-defined adverse events, all randomized patients will be included in the safety population if they received at least one dose of the randomized study drug, and had at least one subsequent safety-related visit.

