† The primary composite endpoint was the first occurrence of any component of the composite of death from all-cause mortality or hospitalization for heart failure in the time-to-event analysis. Data for all endpoint events, irrespective of whether the event was the patient's first occurrence of the event, are shown

Table 3 Endpoint assessment

75

76

77

78

It is expected that the Quality of Life (EQ-5D-3L) data will be reported in secondary publications:

79

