## 11. Evaluation of safety parameters

### ff. Adverse events

Specific adverse events (AE) will be documented and investigated only during the course of

	Intervention arm (N=)	Standard of care arm (N=)
--	--------------------------	------------------------------

---

the index hospitalization (see “11.1.1.Brief summary of adverse events”). Additionally, during the first 180 days, all serious adverse events (SAEs) as defined by current Good Clinical Practice standards will be collected, fully investigated and documented in source documents and case report forms (CRF). Study duration encompasses the time from when the participant signs the informed consent until the last protocol-specific procedure has been completed (last FU at 360 days).

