### **iii. Analysis of adverse events**

Intention- To -Treat (ITT): adverse events will be reported as rates: total nr of events per patient and compared intervention arm vs standard of care arm using Chi square test with two-sided p-values.

Safety population are the patients who received at least once the study drugs (hydralazine and/or nitrates in the form of capsules, spray and/or transdermal application), and events are reported up to last confirmed intake of the study drug.

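### The per-protocol set requires a 180-day assessment and study completion without saying that death satisfies them, so it can select on the outcome; separately, the safety population is defined two ways

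*Combined protocol and SAP*

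**What the plan says.** **Per-protocol set.** SAP 5.4 takes randomised patients who were dosed at least once with hydralazine or a nitrate and who "had a baseline plus follow-up assessment (180 days) of the primary endpoint completing the study without major protocol deviations". A footnote limits major deviations to exclusion criteria that come to light after enrolment. The role of the set is stated: "PP analyses are planned as part of sensitivity analyses". SAP 6.5 describes what appears to be the same sensitivity analysis simply as patients without a major deviation, with no assessment or completion condition.

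**Endpoint.** SAP 2.1 states: "The primary endpoint is death or heart failure re-hospitalization up-to 180 days of follow-up". The footnote to SAP Table 3 makes it the "first occurrence of any component of the composite of death from all-cause mortality or hospitalization for heart failure".

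**Primary analysis set.** SAP 5.3 includes everyone randomised. Patients with no six-month assessment are censored at their last available information.

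**Safety population.** SAP 5.6 requires a dose and that the patient "had at least one subsequent safety-related visit". SAP 11.1.3 defines the set again: "Safety population are the patients who received at least once the study drugs". The second definition has no visit condition.

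**The concern.** A per-protocol set should be defined by eligibility and treatment received. This one is also defined by what happens afterwards. A patient dosed on day 1 who dies on day 60 has no 180-day assessment and has not obviously completed the study. A patient readmitted on day 30 and alive at day 180 meets both conditions. If the first is excluded and the second kept, the analysis compares heart-failure readmission among survivors. It could then neither support nor contradict an intention-to-treat result on death or readmission.

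The SAP leaves the choice to whoever builds the analysis set, possibly after outcomes are known. The two safety definitions leave a similar choice open, on a smaller scale.

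**Working it through.** **1. Does the plan's own non-assessable figure include deaths?** SAP 3.2 needs 385 per arm (770) and plans for about 780 to cover 1–2% who cannot be assessed at 180 days. Check: 770/0.99 = 778 and 770/0.98 = 786, which agrees. In patients, 1–2% of 780 is 8 to 16.

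**2. Deaths by day 180.** Input: 50% mortality at three years (SAP 1). Assumption: constant hazard.
- 1 − 0.5^(180/1095) = 0.108.
- 0.108 × 385 gives about 41 per arm, or about 83 of 770.

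Eighty-three deaths do not fit within 8 to 16 patients, so SAP 3.2 does not treat deaths as non-assessable. SAP 5.4 does not carry that meaning over in words.

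**3. Share of the endpoint lost on the literal reading.** Every patient who dies by day 180 is an endpoint patient, whether or not a readmission came first. The share lost is therefore deaths divided by endpoint patients. The documents give no control event rate. A rate of 50% falling to 40% is assumed because it nearly returns the stated 385 (388 per arm by two proportions, 381 by Freedman, 376 by Schoenfeld). That implies 770 × 0.45 = 346.5 endpoint patients.

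| Assumed 180-day mortality | Deaths of 770 | Share of endpoint patients |
|---|---|---|
| 10.8% | 83 | 24% |
| 15% | 116 | 33% |
| 20% | 154 | 44% |

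**4. Effect on the comparison, literal reading.** Assume mortality of 10.7% in control and 16% with intervention, no effect on readmission, readmission risk r, and independence. Intention-to-treat risk is 1 − (1 − d)(1 − r), where d is mortality. Among survivors it is r in both arms.
- r = 20%: 0.286 and 0.328, ratio 1.15.
- r = 30%: 0.375 and 0.412, ratio 1.10.
- r = 40%: 0.464 and 0.496, ratio 1.07.
- Survivors only: ratio 1.00 in each case.

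The assumed mortality difference vanishes from the per-protocol ratio.

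**5. If a known death counts as assessed.** Patients lost event-free before day 180 are still removed, while those lost after an event can stay. With 1–2% lost, observed risk rises by a factor of at most 1/0.98 = 1.02 in an arm. With 1% lost in one arm and 2% in the other, the risk ratio shifts by 0.99/0.98 = 1.01. This is small, but it departs from SAP 5.3 for no gain.

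**6. Safety population.** The schedule row "Actively search for AE's/ SAE's" (SAP 3.5) is marked at D2, D3 and D6, then at 90, 180 and 360 days. On the same hazard, 770 × (1 − 0.5^(2/1095)) is about 1 death in the first two days and about 3 in the first seven. A higher early hazard would give more.

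**The case against.** The strongest reply is that exclusion of deaths is not the only reading of SAP 5.4. The assessment it asks for is of the primary endpoint, not of a living patient. SAP 2.3 obtains deaths from family physicians, charts and the mortality registry. SAP 3.2 and 6.6.5 attribute missing 180-day assessments to loss, withdrawal or missing adjudication documents, never to death. That is a fair reading and step 1 supports it. But SAP 5.4 does not state it, it does not settle what completing the study means for someone who has died, and step 5 applies even if it is accepted.

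A reader might infer more than the documents support:

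- **That half of the endpoint is lost.** No document gives the split. Step 3 yields 24–44%, on assumed rates.
- **That completion means day 360.** SAP 11.1 runs study duration "until the last protocol-specific procedure has been completed (last FU at 360 days", which would raise the excluded deaths to about 20.4%, or 78 of 385. That sentence defines study duration in the adverse-event section, while SAP 5.4 names 180 days. The link is possible but not stated.
- **That the per-protocol result would reverse direction.** Adding a shared gamma frailty to the 30% scenario gives 1.09 by intention to treat and 0.97 among survivors. The reversal comes from the assumed frailty; without it the survivor ratio is 1.00. With about 344 and 323 survivors, 0.97 has a 95% interval of about 0.75 to 1.25.
- **That the trial could conceal a mortality harm.** All-cause mortality at 180 days is a separate intention-to-treat endpoint (SAP 2.2, 5.3, Table 3), and death has its own row in the adverse-event table.
- **That the safety population drops patients who die in general.** It loses only those who die after a dose and before any safety-related visit. If the vital-sign checks from 30 minutes onward count as such visits, that is almost nobody.

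**Conclusion.** The concern stands in a limited form. SAP 5.4 makes membership depend on follow-up conditions that death can prevent, and it does not say how death is handled. On the literal reading about 41 of 385 randomised patients per arm leave the set, and the fatal component goes with them. On the favourable reading, a bias of about 1–2% from event-free losses remains. The consequence is confined to a planned sensitivity analysis.

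The figure of 41 rests on a constant hazard and on the randomised arm size. The dose condition may make the actual per-protocol base smaller, particularly in control, where the protocol does not require nitrates or hydralazine. That is a separate question, not settled here.

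The two safety definitions conflict as written. The number affected is very small, but any deaths lost would be early ones after dosing, which matter most for safety.

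**What to change.** - **SAP 5.4:** delete the 180-day-assessment and study-completion conditions. Keep the existing dose and major-deviation criteria, and do not add an adherence criterion that the SAP does not define. State that death is an event on its date and that event-free patients are censored at last contact, as in SAP 5.3.
- **SAP 6.5:** refer to the set in SAP 5.4, so that one definition serves this sensitivity analysis.
- **SAP 5.6 and 11.1.3:** use one safety-population definition without the visit condition.

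A single sentence saying that an endpoint event by day 180 counts as assessed and completed would settle the deaths, but it would still drop event-free patients lost early. Deleting the conditions deals with both.

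The cost is SAP wording before the analysis. No new data are needed. On the literal reading the per-protocol set grows by the deaths and early losses it would otherwise exclude.

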### **o. As Treated (AT)**

The as treated population AT consist of all the patients randomized analyzed not to the allocation group but according to the treatment they actually received. No AT analyses are currently planned.

### **p. Safety population**

For the analysis of safety, including protocol pre-defined adverse events, all randomized patients will be included in the safety population if they received at least one dose of the randomized study drug, and had at least one subsequent safety-related visit.

### **q. Definition of sub-group populations in different analyses**

Predefined subgroups are as follows: patients younger versus older than 75 years of age, men versus women, HF with reduced LVEF (LVEF< 40%) versus HF with mid-range LVEF (LVEF 40-49%) versus HF with preserved LVEF (LVEF≥50%), systolic blood pressure at randomization lower versus ≥120 mmHg, coronary artery disease present or not, BNP

---

 Major protocol deviations defined as the disclosure of exclusion criteria after enrollment.

concentration at randomization lower or  $\geq 1000$  pg/ml, patients with versus without known chronic heart failure, and estimated glomerular filtration rate  $< 60$  ml/min versus  $\geq 60$  ml/min.

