### **8.2 Statistical Analysis**

The statistical analyses will be performed using the SPSS / PC (version 14.0, SPSS Inc., USA) software package. A statistical significance level (p-value) of 0.05 will be used. All data will be analyzed on an intention-to-treat basis. Comparisons will be made using the t-test, Mann Whitney U-test, Fisher's exact test, survival analysis (Kaplan Meier method), Cox regression analysis and chi-square test as appropriate. All hypothesis testing will be two-tailed. Statistical support will be performed by [name] from the Institute of Social and Preventive Medicine of the University of Basel.

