### **f. Sample size**

Sample size calculation is based on the on the data from the BASEL V study. A hypothesized 20%-decrease of the composite endpoint death or HF re-hospitalization at 180 days, will require 385 patients per treatment arm to obtain, with a probability of 80%, a log rank test result that is statistically significant at the 5%-level. In order to compensate for an expected 1-2% of patients in whom the primary endpoint could not be assessed at 180 days due to loss to follow-up or complete withdrawal of ICF, it was planned to enroll approximately 780 patients.

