**ii. Adjustments for covariates**

The primary analysis will be adjusted for four strong predictors of the composite primary endpoint (death or HF-rehospitalisation within 6 months): age, HF hospitalization in the year before inclusion, systolic blood pressure, and serum creatinine.

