**vii. Examination of subgroups**

Time to primary endpoint of intervention arm vs standard of care arm will be explored for all the patients and again for the predefined subgroups plus interaction test HR within groups.

---

 Voors, AA, Ouwerkerk, *et al.* Development and validation of multivariable models to predict mortality and hospitalization in patients with heart failure. *Eur J Heart Fail* 2017; 19: 627– 634.

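### Treatment interactions with age, systolic pressure and eGFR are tested only on two-group splits; a treatment-by-continuous-value term should be prespecified beside them

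*Combined protocol and SAP*

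**What the plan says.** SAP 5.7 (lettered q in the body) defines the subgroups. It gives "patients younger versus older than 75 years of age, men versus women", then systolic pressure at randomization split at 120 mmHg, and "estimated glomerular filtration rate" split at 60 ml/min. It cites no source or rationale for these three cuts.

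SAP 6.6.7 (vii) explores time to the primary endpoint in all patients and "again for the predefined subgroups plus interaction test HR within groups". SAP 10.1.2 says the interaction test is between treatment group and the subgroup variables.

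SAP 6.6.2 (ii) adjusts the primary analysis for "age, HF hospitalization in the year before inclusion, systolic blood pressure, and serum creatinine". This puts age and systolic pressure in the model as main effects only. It does not say whether they enter as continuous values, and it adds no interaction with treatment.

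Protocol 2.2 also splits age at 75, but cuts systolic pressure at presentation at 140 mm Hg and lists no eGFR subgroup. SAP 6.6.4 (iv) treats all secondary analyses as explorative and does not read their p-values against a significance threshold.

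**The concern.** Age, systolic pressure and eGFR are all available as numbers at baseline. After the split, 121 and 200 mmHg count as the same pressure, while 119 and 121 count as different. If the treatment effect changes gradually with the covariate, that discards information in tests that are already weak, because the trial is sized for the main effect.

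Systolic pressure is the modifier of most interest, since the intervention is titrated on it. It is also the one whose cut differs between the two documents: 140 mm Hg at presentation in the protocol, 120 mmHg at randomization in the SAP. The treatment schedule (protocol Figure 5a) uses other edges again: 130 at admission, then 110, 130 and 150. An interaction result tied to one of these edges can change with the choice of edge.

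**Working it through.** **1. The plan's own figure.** The only power statement concerns the primary endpoint. "A hypothesized 20%-decrease of the composite endpoint death or HF re-hospitalization at 180 days" "will require 385 patients per treatment arm" "with a probability of 80%, a log rank test result that is statistically significant at the 5%-level" (SAP 3.2), and protocol 8.2 states "All hypothesis testing will be two-tailed". The control event rate is not given. Reading the 20% as a relative risk reduction and solving the Schoenfeld formula for 385 per arm gives:

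- control risk about 49.3%, treated risk 0.8 × 49.3% = 39.5%
- HR = ln(1 − 0.395)/ln(1 − 0.493) ≈ 0.74
- events = 4 × (1.960 + 0.842)² / (ln 0.74)² ≈ 342
- patients per arm = 342/(0.493 + 0.395) ≈ 385

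So 385 per arm is consistent with about 342 events, but only under that back-solved rate. Nothing comparable can be reproduced for the interaction tests. The documents state no interaction size, no interaction power and no share of patients on either side of any cut.

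**2. Information kept by a split.** Assume a normal covariate with effect modification linear in it, cut at quantile q:

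e = φ(z_q)² / [q(1 − q)]

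- median: 0.3989²/0.25 = 0.637
- 30/70: 0.3477²/0.21 = 0.576
- 20/80: 0.2800²/0.16 = 0.490

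On 342 events, a median split is like testing the interaction on 342 × 0.637 ≈ 218 events.

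**3. Power after the split.** Power = Φ[(1.96 + z_power)√e − 1.96]. For 80% with the continuous term:

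- median: 2.802 × 0.798 − 1.96 = 0.275, so 60.8%
- 30/70: 2.802 × 0.759 − 1.96 = 0.166, so 56.6%
- 20/80: 50.0%

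Starting from 50% the results are 34.6% (median) and 31.8% (30/70). Starting from 20% they are 14.3% and 13.3%.

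**4. Trial scale.** Use SE of the interaction log hazard ratio per SD = 2/√events, with 250 to 400 events as an assumed range. Worked example, 400 events and a hazard-ratio ratio of 0.85 per SD:

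- SE = 0.100 and |ln 0.85|/SE = 1.625
- continuous power = Φ(1.625 − 1.96) = 36.9%
- after a median split, Φ(1.625 × 0.798 − 1.96) = 25.4%

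| HR ratio per SD | Continuous power, 250 / 400 events | Median split | 30/70 split | Loss (points) |
|---|---|---|---|---|
| 0.90 | 13.0 / 18.2% | 9.8 / 13.1% | 9.2 / 12.3% | 3–6 |
| 0.85 | 25.0 / 36.9% | 17.5 / 25.4% | 16.2 / 23.4% | 8–14 |
| 0.80 | 42.2 / 60.7% | 29.0 / 42.9% | 26.7 / 39.5% | 13–21 |
| 0.75 | 62.3 / 82.0% | 44.2 / 63.1% | 40.7 / 58.8% | 18–23 |

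**5. Simulation check.** Cox models with 770 patients, a 49% control rate, HR 0.74, a standard normal covariate, about 345 events and 2,500 runs per setting:

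| Interaction, log HR per SD | Median cut | 30/70 cut |
|---|---|---|
| 0.1 | 15.4 → 10.9% | 15.2 → 9.2% |
| 0.2 | 47.4 → 30.8% | 44.6 → 22.8% |
| 0.3 | 77.6 → 55.6% | 78.0 → 47.0% |

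The pattern agrees with the formulas. The simulated loss is somewhat larger for strong interactions.

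**6. The reverse case.** If the true modification is a step exactly at the cut, the same e applies to the linear term. A step at the median that the split detects with 80% power is detected with about 61% power by a linear term.

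**The case against.** The strongest reply is that prespecified categories are a legitimate choice, that the SAP calls these analyses explorative, and that it does not judge their p-values against a threshold. Power at 5% is then not a criterion the plan uses. This stands, and it keeps the point minor. It does not remove the loss of precision, however, and a p-value read as a graded measure gains from a more efficient test.

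Second, a step is not far-fetched for systolic pressure, because dosing goes by pressure bands. In that case the split wins by about as much as it loses under linearity. This also stands, and it is why the continuous term should accompany the category test and not replace it. The dosing bands have no edge at 120 mmHg, though, so they do not support a step at that particular cut.

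Third, normality is doubtful. Protocol 4.2 excludes systolic pressure below 100 mm Hg at presentation and chronic kidney disease with creatinine above 250 µmol/l, so the systolic pressure and eGFR distributions are likely to be truncated. The percentages are therefore illustrations.

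Fourth, BNP and LVEF are also continuous values cut into groups. That is fair, and the same supplement could be added for them. They are left out here because the BNP cut is also the randomization stratum and LVEF is reported in three classes.

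A reader might infer a fixed cost to this trial of some 16 to 23 points of power. The documents do not support that. Such a range needs a continuous test with about 50 to 90% power and a cut between about the 30th and 50th percentile, besides linearity and normality, and none of these is given.

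**Conclusion.** The point holds as an inexpensive improvement. The three interactions are tested only on two-group splits, and for systolic pressure the two documents use different cuts without explanation. Under linear modification in a normal covariate, a median split keeps about 64% of the information and a 30/70 split about 58%. The power cost is about 3 to 14 points for modest interactions (hazard-ratio ratio 0.90 to 0.85 per SD, 250 to 400 events assumed). It is larger for strong interactions or for cuts far from the median, and it reverses if the truth is a step at the cut.

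Two further inferences would go too far. The category tests are not invalid, and the primary analysis is not affected. Nor do the differing systolic cuts show which one is wrong. They show only that the subgroup answer depends on the choice.

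**What to change.** In SAP 6.6.7, keep the listed categories and their interaction tests for the forest plot. For age, systolic pressure and eGFR, prespecify in addition a treatment-by-continuous-value term in the primary Cox model, linear, with a restricted cubic spline as a check. Report it beside the category test and show the hazard ratio as a curve over the baseline value. eGFR is not among the four adjustment covariates (serum creatinine is), so its own main effect must be in that fit. State in SAP 5.7 why the systolic cut and time point differ from protocol 2.2.

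The cost is three extra interaction models with their spline checks, and one figure, on data already collected. The downside is that a linear term has less power than the split if the effect changes abruptly at the cut. Reporting both covers that case. The analyses should remain labelled explorative.

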### 4.2 Exclusion Criteria

- Cardiopulmonary resuscitation less than 7 days ago.
- Cardiogenic shock, ST-elevation myocardial infarction, or other clinical conditions that require immediate ICU admission or urgent PTCA.
- Systolic blood pressure lower than 100 mm Hg at presentation.
- Primary rhythmogenic cause of acute decompensation (ventricular tachycardia, reentry tachycardia, atrial fibrillation or atrial flutter with a ventricular rate exceeding 140 beats per minute).
- Non-ST-elevation myocardial infarction as primary diagnosis.
- Severe aortic or mitral stenosis.
- Adult congenital heart disease as primary cause of acute HF.
- Hypertrophic obstructive cardiomyopathy.
- Isolated right ventricular failure due to pulmonary hypertension.
- Chronic kidney disease with creatinine levels  $> 250$   $\mu$ mol/l.
- Bilateral renal artery stenosis.
- Severe sepsis or other causes of high output failure.
- Liver Cirrhosis Child-Pugh class C.
- Systemic Lupus erythematosus and related diseases.
- Acute aortic dissection.

- Porphyria.
- Previous adverse reactions to nitrates.
- Known hypersensitivity to hydralazine or dihydralazine.
- Patient in an emergency situation resulting in an inability to give informed consent.

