## **7. Study Withdrawal**

A) Discontinuation of participation of the patient due to withdrawal of consent

B) Discontinuation of participation due to:

- a) disclosure of exclusion criteria after enrolment;
- b) occurrence during participation in study of a serious new clinical event which contraindicates vasodilatation, e.g. acute stroke, acute traumatic brain injury with cerebral edema;
- c) decision of the treating medical team to switch towards palliative care

If there are findings that indicate that a further participation in the study would lead to a disproportionate risk for the patient’s health or life, the patient may be excluded from the study.

In case of an adverse event or a serious adverse event (e. g. symptomatic hypotension, acute coronary syndrome, acute kidney injury etc.) or known or unexpected side effects related to the study medication the treatment with the concerning medication will be adjusted or suspended. All other procedures remain unaffected and the patient will not be excluded from the study.

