### **v. Methods for handling missing data and sensitivity analyses**

Sensitivity analyses will be conducted in: patients without evidence of systemic, infection/inflammation at presentation (defined as CRP  $< 20$  mg/L), in patients without major protocol deviation and in patients enrolled in outside Europe and Central Europe.

To deal with data with  $> 10\%$  missing values, sensitivity analyses will be conducted using multiple imputations by chained equations methods and 20 data-sets will be created.

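### The SAP's only major protocol deviation is an exclusion criterion found after enrolment, so its per-protocol and no-deviation analyses say little about adherence

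*Combined protocol and SAP*

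**What the plan says.** SAP 5.4 builds the per-protocol set from randomised patients "who received at least one dose of the study drug". Study drug there means hydralazine or nitrates in any of the listed forms. The patient must also have a baseline assessment and a "follow-up assessment (180 days) of the primary endpoint completing the study without major protocol deviations". On its role, the SAP states that "PP analyses are planned as part of sensitivity analyses".

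Footnote 2 is called from SAP 5.4 and printed at the foot of the subgroup section (SAP 5.7). It reads: "Major protocol deviations defined as the disclosure of exclusion criteria after enrollment". Nothing else in either document extends the term to crossover, contamination, missed titration or low exposure. The wording matches withdrawal reason B(a) in protocol section 7, "disclosure of exclusion criteria after enrolment".

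SAP 6.5 uses the same term for a separate sensitivity analysis, "in patients without major protocol deviation", with no dose or follow-up condition. SAP 5.5 states that no as-treated analysis is planned. The primary analysis is by intention to treat, whatever drug was received (SAP 5.3 and 6.6.5).

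**The concern.** A per-protocol analysis is normally read as the effect among patients treated as the protocol intended. Here the definition looks at eligibility and hardly at treatment.

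It also removes patients on an event that happens after randomisation, in a trial where the ward staff know the arm (SAP 3.4). Some listed exclusions bear on the study drugs, for example "Bilateral renal artery stenosis", severe aortic or mitral stenosis, and hydralazine hypersensitivity. Such a condition could come to light because of how a patient responds to treatment. Nothing limits removal to facts present at baseline, and nothing requires the judgement to be made blind to arm.

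What is at stake is interpretation. Readers tend to take agreement between per-protocol and intention-to-treat results as evidence of robustness. With these definitions, agreement would carry little information about adherence.

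**Working it through.** The plan gives no figure for this point, so the main check is of the text. The arithmetic after it only illustrates scale.

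**Step 1: who stays and who goes**

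| Patient | Per-protocol set (SAP 5.4) | No-deviation analysis (SAP 6.5) |
|---|---|---|
| Intervention: one dose, then off schedule with no protocol reason, followed to day 180 | kept | kept |
| Intervention: no nitrate or hydralazine at all | dropped (one-dose rule) | kept |
| Control given the intervention drugs, followed to day 180 | kept | kept |
| Control given no nitrates, as Figure 5b allows (0 to 10 mg) | dropped, read literally | kept |
| Exclusion criterion found after enrolment | dropped | dropped |
| Death before day 180 | unclear | kept |

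Read literally, then, the per-protocol set can keep a contaminated control and drop a compliant one.

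**Step 2: dilution from crossovers who are kept**

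Assumptions: the true risk ratio is 0.80 (the plan's 20% decrease, read as relative); a fraction c = 0.15 of each arm crosses over; crossovers take the other arm's risk and are otherwise typical. The documents give no crossover rate.

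- Control risk: p(1 − 0.15 × 0.20) = 0.97p.
- Intervention risk: p(0.80 + 0.15 × 0.20) = 0.83p.
- All crossovers kept: 0.83/0.97 = 0.856, an observed reduction of 14.4%. This applies to SAP 6.5, and to SAP 5.4 if every crossover had at least one dose.
- Intervention crossovers who took no study drug are dropped from SAP 5.4: 0.80/0.97 = 0.825, a reduction of 17.5%. That recovers (17.5 − 14.4)/(20 − 14.4) = 3.1/5.6, a little over half of the loss.
- If the one-dose rule also drops a fraction z of controls who rightly had no nitrates, the contaminated share of the remaining controls rises from c to c/(1 − z), and dilution increases. The documents give no value for z.

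With c = 0.05, 0.10 and 0.20 and everyone kept, the observed reductions are 18.2%, 16.3% and 12.5%.

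**Step 3: removal that differs by arm**

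If a fraction e of an arm is removed and those patients have event risk r, the remaining risk is (p − e·r)/(1 − e). Assume no true effect, r = 0.60, and 1% of controls removed. The plan does not state a control risk. Read as a relative fall in risk, 385 per arm at 80% power corresponds to about 0.50, so that value is shown beside 0.25 and 0.35. The standard error of the log risk ratio is √(2(1 − p)/(385p)): 0.125, 0.098 and 0.072 for p = 0.25, 0.35 and 0.50.

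| p | Control, e = 1% | Intervention, e = 3% | Ratio | Intervention, e = 5% | Ratio |
|---|---|---|---|---|---|
| 0.25 | 0.2465 | 0.2392 | 0.970 | 0.2316 | 0.940 |
| 0.35 | 0.3475 | 0.3423 | 0.985 | 0.3368 | 0.969 |
| 0.50 | 0.4990 | 0.4969 | 0.996 | 0.4947 | 0.991 |

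The largest shift, ln(0.940) = −0.062, is about 0.5 standard errors; ln(0.985) = −0.015 is about 0.15. Exchanging the removal rates between arms inverts each ratio, so the sign depends wholly on which arm has more late findings.

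**The case against.** The strongest reply is that little depends on this. The primary and secondary endpoints are analysed by intention to treat, the per-protocol analysis is only supportive, and removing ineligible patients is a usual per-protocol rule. All of that stands, and it limits the weight of the point.

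A reader might infer several stronger things that the documents do not support:

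- **That both analyses tilt towards the intervention by removing patients it harmed.** No passage shows more late findings in that arm. The prescribed responses to hypotension and rising creatinine are dose changes and monitoring, not a search for exclusion criteria. Creatinine is measured periodically in both groups, controls also start an ACE-inhibitor or ARB, and echocardiography is expected in most patients. The literal one-dose rule adds a further selection of controls, whose net effect is unknown.
- **That the per-protocol set recovers none of the dilution.** It drops intervention patients who had no dose, so in Step 2 it can recover part.
- **That these are the only checks on adherence.** Blood pressure course over six days, medication by arm at follow-up, and the share of adverse events at which the intervention was stopped are also planned. They are descriptive but informative.
- **That anyone who stopped is a deviator.** The protocol itself directs reductions, suspensions and the withholding of hydralazine in defined circumstances. Keeping those patients is right in a trial of a strategy.
- **That early deaths are certainly dropped.** Death is the primary endpoint, and the SAP attributes an unassessable endpoint to withdrawal, loss to follow-up or missing adjudication documents. The wording is unclear rather than wrong.

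What survives is the definition itself: it omits treatment received, and it is not tied to baseline facts or to blinded judgement.

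**Conclusion.** The point holds for the two supportive analyses and leaves the intention-to-treat primary result untouched. Three conclusions follow from the text alone:

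- Departures from treatment are not major deviations, so treated non-adherent patients and contaminated controls remain in both analyses.
- Eligibility removals rest on an unblinded finding after randomisation that could differ by arm.
- The one-dose rule, read literally, removes compliant controls.

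Agreement of either analysis with intention to treat would therefore say little about adherence.

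The sizes rest on assumed rates. Crossover of 5% to 20% in each arm, all kept, takes a true 20% reduction to between 18.2% and 12.5%. Unequal removal of 3% or 5% against 1% moves a null ratio to between 0.940 and 0.996, at most about half a standard error. The actual direction and size of any bias cannot be settled from the documents.

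**What to change.** Revise footnote 2 and SAP 5.4, and have SAP 6.5 refer to the same definition:

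- Remove a patient for ineligibility only if the criterion was present, and documented or measurable, from data recorded before randomisation. Judge this blind to arm and outcome.
- Add arm-specific departures from the protocol's own treatment schedule: Figure 5a for the intervention arm, and Figure 5b with the limits under Study Therapy Control Group for controls. Exempt reductions, suspensions and withholding that the protocol directs. The sponsor should first clarify whether the control-arm sentence on higher doses covers any hydralazine or only higher doses of it.
- Apply the one-dose condition to the intervention arm only.
- State that death or heart failure re-hospitalisation before day 180 meets the 180-day assessment and completion requirements.

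The cost is SAP wording and a blinded deviation review before database lock. The downside is that the per-protocol set may become smaller, and it remains a non-randomised, supportive comparison.
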